Objectives	recognition in quiet after remote fitting is no worse than
	speech recognition in quiet after in-office fitting.

Primary Study/Efficacy Endpoints	The primary efficacy endpoint are the chronic remote fitting AzBio sentence scores in quiet at Visit 3 as compared to chronic in-office fitting AzBio sentence scores in quiet at Visit 2.		
Safety Objective	The safety objective is absence of unanticipated adverse device effects related to remote fitting.		
Supporting Data	
 
Analysis of subjective outcome measures
 
Analysis of custom subject remote fitting satisfaction questionnaire
 
Analysis of custom audiologist remote fitting satisfaction questionnaire
 
Analysis of subject reimbursement questionnaire
 
Analysis of acute speech perception data
 
Analysis of in-office fitting vs remote fitting duration
 
Analysis of psychophysical data
 
		
Study Schedule & Duration	
 
Visit 1:         
 
Informed Consent/Assent
 
Demographics & Audiological History
 
Mobile Device Proficiency Questionnaire
 
Reimbursement Questionnaire
 
Audiometric Thresholds
 
Speech in Quiet, Personal Sound Processor
 
Confirmation of Eligibility
 
Naída CI M DS Sound Processor In-Office Fitting
 
Acute Speech in Quiet, Naída CI M DS Sound Processor
 
 
 
		
	
 
Visit 2: 2-3 weeks after Visit 1
 
Subjective Outcome Measure Questionnaire
 
Chronic Speech in Quiet, Naída CI M DS Sound Processor
 
Naída CI M DS Sound Processor Remote Fitting via Smart Phone App
 
Acute Speech in Quiet, Naída CI M DS Sound Processor
 
Custom Subject Remote Fitting Satisfaction Questionnaire
 
Custom Audiologist Remote Fitting Satisfaction Questionnaire
 
		
	
 
Visit 3: 2-3 weeks after Visit 2
 
Subjective Outcome Measure Questionnaire
 
Chronic Speech in Quiet, Naída CI M DS Sound Processor
 
		

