#### 7.2.3 **Safety**

Adverse event data will be collected and evaluated during the study to ensure that the safety of patients is maintained as per requirements of an IDE and respective center Institutional Review Board guidelines for reporting. The primary safety endpoint is the absence of unanticipated adverse device effects related to remote fitting.

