#### 8.2.4 Safety Endpoint

The safety objective is the absence of unanticipated adverse device effects related to remote fitting.

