#### 9.1 Adverse Event Definitions and Classifications

#### 9.1.1 Serious Adverse Event

A serious adverse event (SAE) is an event that: a) led to a death, or b) led to a serious deterioration in the health of the subject that:

- resulted in a life-threatening illness or injury,
- resulted in a permanent impairment of a body structure or of a body function,
- required inpatient hospitalization or prolongation of existing hospitalization,
- resulted in medical or surgical intervention to prevent permanent impairment to body structure or a body function, or
- led to fetal distress, fetal death or a congenital abnormality or birth defect.

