#### 9.1.2 Adverse Device Effect and Serious Adverse Device Effect

An adverse device effect (ADE) is any untoward and unintended response to a medical device. A serious adverse device effect (SADE) is an event related to the device that resulted in any of the consequences characteristic of a serious adverse event (SAE) or that might have led to any of the consequences if suitable action had not been taken or interventions had not been made or if circumstances had been less opportune.

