#### 9.1.3 Unanticipated Adverse Device Effect

An unanticipated adverse device effect (UADE) is any serious adverse effect on health or safety; any life threatening problem or death caused by, or associated with, a device, if that effect, problem, or death was not previously identified in nature, severity, or degree of incidence in the investigational plan or application; or any other unanticipated serious problem associated with a device that relates to the rights, safety, or welfare of subjects.

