#### 9.3 Anticipated Adverse Events

The risks associated with the investigational products include but are not limited to:

- There is a possibility that speech and environmental sounds may sound different or louder than what the subjects are accustomed to hearing or that subjects may not like the sound quality of the study sound processor used in the study. This risk occurs with all changes to sound-processing, and subjects should be advised of this possibility. If a subject cannot tolerate using the study sound processor or does not like the sound quality, they can return to using their own sound processor with their baseline programming. In this event, the subject will be withdrawn from the study.
- Subjects may experience some overly loud sounds that result in discomfort. If such loud sounds occur, they can be stopped immediately by removing the headpiece and/or the entire external device.
- Subjects may experience neural tissue damage in the event of chronic overstimulation.
- There is risk of facial nerve stimulation. This risk can be mitigated through reprogramming of the device.
- Subjects may experience intermittent sound or short-term loss of functionality while
  wearing the device or while being programmed. The intermittency can be eliminated by
  changing the headpiece, reprogramming the sound processor, or exchanging the sound
  processor.
- Subjects may have permanent residual acoustic or natural hearing damage due to excessive acoustic power.
- Subjects may experience skin or tissue irritation because of the device materials or the equipment may overheat or otherwise malfunction, causing tissue damage.
- Subjects will be exposed to small parts that pose a choking hazard. Care should be taken to avoid choking and the outcomes of choking, such as endoscopic surgery or death.
- Exposure to electromagnetic emissions from the device (external sound processor, internal device) may adversely interfere with other electronic medical devices
- Subjects should only use accessories compatible or designed for the study sound processor (such as the battery chargers) in order to avoid electric shock.
- Static electricity can potentially damage sensitive electronic components such as the ones used in the cochlear implant system.

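### The safety objective counts only UADEs, so a serious remote-fitting-related effect matching a listed risk could leave it met, and the stated subject-level AE summary does not separate remote from in-office exposure

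*Combined protocol and SAP*

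**What the plan says.** The safety criterion appears three times with the same content. The synopsis says "The safety objective is absence of unanticipated adverse device effects related to remote fitting", section 7.2.3 says "The primary safety endpoint is the absence of unanticipated adverse device effects related to remote fitting", and section 8.2.4, under the analyses, says "The safety objective is the absence of unanticipated adverse device effects related to remote fitting". None of the three adds a second component, a rate limit or a comparison.

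Section 9.1.3 limits a UADE to a serious effect, problem or death that "was not previously identified in nature, severity, or degree of incidence in the investigational plan or application". It also takes in any other unanticipated serious problem associated with the device. Section 9.3 lists risks of the investigational products, refers to Appendix A for the full list, and treats all listed risks as anticipated adverse events. One entry reads "Subjects may experience neural tissue damage in the event of chronic overstimulation". Another is permanent damage to residual or natural hearing from excessive acoustic power.

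Under 9.1.1 an event is serious if, among other things, it "resulted in a permanent impairment of a body structure or of a body function". Section 9.1.2 makes such an event a SADE when it is device-related, and extends the term to an event "or that might have led to any of the consequences if suitable action had not been taken or interventions had not been made".

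Section 9 summarises adverse events as the number and percent of all subjects, broken down by event type, status and frequency. Section 9.3 adds that the incidence of anticipated events will be reported with the results.

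**The concern.** Section 3 states the goal of demonstrating that remote fitting is safe as well as effective, and section 5 calls the study pivotal. Several serious listed risks concern what a fitting session sets. Section 7.4.3 has the audiologist program M levels remotely and, for acoustic earhook users, review gains; section 9.3 names chronic overstimulation and excessive acoustic power as sources of harm. Harms tied closely to the investigational act may thus be the ones left out of the criterion. The clinical report could then state that the safety objective was met with a serious remote-fitting-related device effect on record.

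The second issue is description. Each subject passes through in-office wear, the remote session, remote wear, and two weeks back on the personal processor. A pooled percentage does not show which events began after the remote session, and that is the comparison a within-subject design can offer.

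**Working it through.** **1. What the criterion counts**

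| Event | SADE (9.1.2)? | UADE (9.1.3)? | Counts against the objective? |
|---|---|---|---|
| Remote-fitting-related, serious consequence, not a listed risk | Yes | Yes | Yes |
| Remote-fitting-related, serious consequence, listed risk, severity or incidence beyond what was identified | Yes | Yes | Yes |
| Remote-fitting-related, serious consequence, listed risk, within what was identified | Yes | No | No |
| Near miss (second limb of 9.1.2), listed risk, within what was identified | Yes | No | No |

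The third row is the gap. Permanent hearing damage meets the permanent-impairment limb of 9.1.1, so if related to remote fitting it is a SADE and could fall in that row. The visible text of 9.3 gives no expected incidence for any listed risk, so the boundary between the second and third rows cannot be fixed from the documents at hand.

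**2. Share of the AE window that is remote wear**

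Inputs: in-office wear *o* = 2 or 3 weeks (7.4.2, 7.4.3); remote wear *r* = 2 or 3 weeks (7.4.3, 7.4.4); 2 further weeks after the last visit (section 9). This assumes consent at Visit 1 and no rescheduled remote session.

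Share = r / (o + r + 2)

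- o = 2, r = 2: 2/6 = 33.3%
- o = 3, r = 2: 2/7 = 28.6%
- o = 2, r = 3: 3/7 = 42.9%
- o = 3, r = 3: 3/8 = 37.5%

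Remote wear is 29% to 43% of the window; the other 57% to 71% is not.

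**3. The zero-event bound in 8.1**

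Exact one-sided 95% upper bound with no events in n subjects = 1 − 0.05^(1/n).

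- n = 17: 1 − 0.05^(1/17) = 0.1616, which reproduces the protocol's 16.2%.
- n = 17 − 4 = 13: 1 − 0.05^(1/13) = 0.2058, or 20.6%.

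The value 13 is a worst case: all 4 dropouts allowed for in 8.1 leave before any remote session starts. The plan sets no acceptance limit for this bound, so the difference affects reporting and no decision.

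**4. What could sit beside a met objective**

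One anticipated remote-fitting-related SADE in 17 subjects is 1/17 = 5.9%, with an exact one-sided 95% upper bound of 25.0% (0.95 quantile of the beta distribution with parameters 2 and 16). The UADE count could still be zero.

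**The case against.** The strongest reply is that such events are already dealt with. Under 9.2, SAEs, SADEs and UADEs go to the sponsor immediately, and an unreasonable risk terminates the study or the affected parts. Section 9.3 promises the incidence of anticipated events. This stands: a reader might infer that serious device effects would go unreported or that subjects are unprotected, and the documents say otherwise. But reporting and stopping rules do not enter the criterion on which the safety conclusion is stated to rest.

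Second, the exemption rests on text that cannot be read here. Appendix A, the application and the remote-fitting risk list introduced in 12.4 are not visible. This also stands. It would go too far to say that any serious harm on the list automatically passes, because unusual severity or incidence brings it back within 9.1.3. The supportable word is *could*.

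Third, the endpoint already concerns only effects related to remote fitting, so the 29% to 43% share cannot change whether it is met. Agreed; that figure bears on the descriptive summary alone. Section 8 also defers detail to the SAP, so the missing split by period is a gap in what is stated, not evidence that no such table is planned.

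Fourth, one might conclude that any SADE should fail the objective. The documents do not support that step. Sections 12.3 and 12.4 accept residual risk on benefit-risk grounds, and a zero-tolerance rule would include no comparison with in-office fitting. It could also fail often. The chance of at least one event in 17 is 1 − (1 − p)^17, which is 15.7% at p = 1% and 58.2% at p = 5% (both rates are assumptions; the documents give none).

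**Conclusion.** The point holds as a recommended improvement. As written, the safety objective could be declared met despite a remote-fitting-related SADE with a serious consequence, provided the event matched a listed risk and did not exceed its identified severity or incidence. That follows from the definitions and depends on no calculated figure. How much room the exemption leaves cannot be sized without the unseen risk lists.

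The pooled subject-level summary is the smaller part. It covers a window that is 57% to 71% something other than remote wear, given the stated visit intervals and no rescheduling.

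A reader might also take the 20.6% bound as a sign that 16.2% is wrong. It is not: 16.2% is correct for 17 subjects, and the larger figure applies only if as few as 13 are exposed. Neither subject protection nor the efficacy analysis is called into question.

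**What to change.** 1. Keep the UADE endpoint. In 7.2.3 and 8.2.4, with the synopsis aligned, add a co-reported safety endpoint: the number and percent of subjects with a remote-fitting-related SADE that resulted in a consequence listed in 9.1.1, anticipated or not. State that the safety conclusion will be drawn from both. List near-miss SADEs (second limb of 9.1.2) separately.

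2. In the SAP, tabulate ADEs and SADEs by relatedness and onset period:
   - in-office wear, from the Visit 1 fitting to the start of the first remote session;
   - remote session or sessions, including any interval up to a rescheduled session that is completed (7.4.3 allows rescheduling);
   - remote wear, from the completed remote fitting to return of the processor;
   - the two weeks after the last visit.

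3. For remote-fitting-related events, use subjects in whom a remote session was started as the denominator. Leave 16.2% in 8.1 as the planning figure and compute the exact bound from the number actually exposed when reporting.

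The cost is a few sentences and one table. Onset date, seriousness and relatedness are already on the CRF (9.2), and no visit or measurement is added. The safety conclusion may turn out less favourable. The change also has a limit: the Schedule of Events places audiometric thresholds at Visit 1 only, so it would count hearing damage that is reported but would not detect it.

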#### 7.3 Study Procedures

Advanced Bionics staff may be present during study procedures for the purpose of guiding investigators with regards to per protocol performance of these procedures. As this potentially involves contact with study subjects, Advanced Bionics staff will conduct these activities in a way that they do not bias data integrity. No study procedures will be performed by Advanced Bionics staff.

#### 7.3.1 Audiometric Measures:

Unaided air conduction hearing thresholds (in dB HL) will be measured for the implanted ear(s) using the centers calibrated audiometer and standard audiometric technique for pure-tone air conduction testing.

Unaided air conduction thresholds using insert earphones at octave and inter-octave frequencies will be obtained (125, 250, 500, 1000, 2000, 3000, 4000 and 8000 Hz).

#### 7.3.2 Speech Perception Measures:

All speech perception testing will be conducted using recorded stimuli presented from a single loudspeaker in, at a minimum, a single-walled sound booth capable of accommodating the calibrated speaker orientation. Soundfield levels will be calibrated to 74 dB SPL using a microphone placed at the approximate position of the subject's head (one meter from loudspeaker).

Speech perception measures in the soundfield are to be administered unilaterally for unilaterally implanted subjects and bilaterally for bilaterally implanted subjects via a loudspeaker at 0° azimuth at a distance of one meter from the subject. Speech signals will be presented at 60 dBA.

Devices will be removed from the non-test ear (if necessary) for unilaterally implanted subjects and foam plugs will be used to isolate the test ear for unilateral users.

#### 7.3.3 AzBio Sentence Test

The AzBio Sentence Test (Spahr et al., 2012) is a validated test of open-set sentence recognition ability. The test will be administered in quiet at 60 dBA (target 0° azimuth). The test is scored as total number of words correct which will be expressed for reporting as percentage correct. The sentence tokens include both male and female speakers.

Acute AzBio sentence testing will be performed immediately following in-office and remote fitting sessions, respectively. Chronic AzBio sentence testing will performed at the beginning of each follow-up visit.

## 7.3.4 Questionnaires

Subjects will be completing a Mobile Device Proficiency Questionnaire (MDPQ-16), subjective outcome measures questionnaires (SSQ-12), a reimbursement questionnaire and a custom remote fitting satisfaction questionnaire. In addition, audiologists will be completing a custom remote fitting satisfaction questionnaire. Questionnaires may be completed on paper or electronically in the EDC system.

#### 7.4 Study Visits and Visit Windows

#### 7.4.1 Schedule of Events

Procedure	Visit 1	Visit 2	Visit 3
Informed Consent/Assent	~		-
Demographics & Audiological History	Y		
Mobile Device Proficiency Questionnaire	>		
Reimbursement Questionnaire	>		
Audiometric Thresholds	Y		
AzBio in Quiet, Personal Sound Processor	>		
Confirmation of Eligibility	Y		
Naída CI M DS Sound Processor In-Office Fitting	>		
Naída CI M DS Sound Processor Remote Fitting via Smart Phone App		•	
Acute AzBio in Quiet, Naída CI M DS Sound Processor	Y	>	
Chronic AzBio in Quiet, Naída CI M DS Sound Processor		>	>
Subjective Outcome Measure Questionnaire (SSQ-12)		>	>
Custom Subject Remote Fitting Satisfaction Questionnaire		✓ &	
Custom Audiologist Remote Fitting Satisfaction Questionnaire		✓ &	
Adverse Event Assessment	>	>	>
Device Accountability	~	~	>
& Only if remarks fitting was accomplying appealated			

& Only if remote fitting was successfully completed

#### 7.4.2 Visit 1

This visit is performed at the audiologist's office.

- After informed consent/assent, subject's demographics and hearing history will be captured.
- Subjects' technical competency will be determined using the Mobile Device Proficiency (MDPQ-16) questionnaire and subjects will complete a Reimbursement Questionnaire.
- Speech perception in quiet will be tested using the subject's personal sound processor to determine eligibility for the study.
- Audiometric thresholds are used to determine whether subjects are considered to have aidable residual hearing (ARH). Subjects not meeting the ARH criteria will be fitted under the electric-only criteria (EO). Audiometric thresholds will be determined for the implanted ear only for unilaterally implanted subjects and for both ears individually for bilaterally implanted subjects.
  - Bilateral subjects meeting the ARH inclusion criteria in both ears will be enrolled in the ARH group. Bilateral subjects meeting ARH criteria in only one ear will be screen failed.
- Subjects who meet inclusion and do not meet exclusion criteria are then fit with a Naída CI M DS sound processor in the audiologist's office. Unilateral ARH subjects will be fitted with an acoustic earhook and EO subjects will be fitted with a T-mic. Bilateral subjects meeting the ARH criteria will be fitted with an acoustic earhook in both ears. Fitting parameters on the Naída CI M DS sound processor should mimic the parameters on the subject's personal sound processor as closely as possible and be adjusted for comfort and sound quality as needed. Program settings will include two programs, one AutoSense OS program with and a second manually selected Calm situation program. This will be considered the in-office fitting.
- Acute speech perception in quiet is performed to confirm the in-office fitting on the Naída CI M DS sound processor.
- Adverse events and device observations are collected, as needed, and device accountability is performed.
- Following the visit, the subject will test the Naída CI M DS sound processor chronically for 2-3 weeks during their day-to-day activities.

#### 7.4.3 Visit 2

Visit 2 will occur 2-3 weeks after Visit 1.

- The visit will start at the audiologist's office with subjects completing a subjective outcome measures questionnaire.
- Chronic speech perception in quiet will be tested using AzBio sentences.
- In addition, the audiologist will introduce the remote fitting application to the subject and will pair the smartphone with the subject's Naída CI M DS sound processor. For the purposes of the study, a dedicated fitting smartphone will be used that is only used for remote fitting.
- The subject will then move to the remote fitting location. The audiologist will initiate the remote fitting session through Target CI DS, and the subject will open the application on the remote fitting smartphone. Both parties will engage verbally to ensure audibility and visualization via smartphone video during the call. The audiologist then remotely connects to the subject's sound processor to begin the fitting session. The fitting will include measurement of impedances, measurement of electrode-specific neural response imaging (NRI), programming of M levels, and live speech stimulation to confirm acceptability of adjustments. Fittings for AHR subjects will include a review of acoustic and electric cutoff frequencies and gains at 65 dB. Additional adjustments may be made as needed to ensure comfort and clarity of the Map and to ensure acceptability of the fitting

during the subject's chronic wear period. The audiologist and subject will then confirm the completion of the fitting and both parties close their respective remote fitting session applications.

- Should technical issues occur during the remote fitting session, the audiologist will first try to mitigate the issues, for example by instructing the subject to turn off their outgoing video or to move to a different location in case of poor connection.
- ➤ The audiologist will re-schedule the remote fitting session should the remote app fitting not be completed because technical issues could not be mitigated during the session. Adverse events and/or device observations are collected and device accountability is performed, as needed.
- ➤ If remote fitting cannot be completed due to non-technical reasons (e.g. subject was not able to sufficiently communicate with the audiologist via the app), the subject will be exited from the study. Reasons for non-completion of the remote fitting will be documented. Adverse events and/or device observations are collected and device accountability is performed.
- After the remote fitting session is successfully completed, the subject will rejoin the audiologist in person for acute speech perception in quiet to confirm the remote fitting on the Naída CI M DS sound processor.
- In addition, the audiologist and the subject each will complete a custom remote fitting satisfaction questionnaire.
- Adverse events and device observations are collected and device accountability is performed, as needed.
- Following the visit, the subject will test the remotely-fitted Naída CI M DS sound processor chronically for 2-3 weeks during their day-to-day activities.

#### 7.4.4 Visit 3

Visit 3 will occur 2-3 weeks after the Visit 2.

- This visit is performed at the audiologist's office and begins with subjects completing a subjective outcome measures questionnaire.
- In addition, chronic speech perception in quiet will be tested.
- Adverse events and device observations are collected, as needed, and device accountability is performed.
- The subject will then return the Naída CI M DS sound processor and return to using their personal sound processor. Standard clinical follow-up is recommended after subjects exit the study.

